**1. Research Background**

Allogeneic-hematopoietic stem cell transplantation (allo-HSCT) is an important protocol for the treatment of benign and malignant hematological diseases such as acute leukemia, severe aplastic anemia, thalassemia, etc. chronic graft versus host disease (cGVHD) is a clinicopathological syndrome caused by donor lymphocytes attacking the recipient's organs in the process of reestablishing donor immunity after allo-HSCT, with an incidence of about 30%-70% [1,2]. The clinical manifestations of cGVHD are diverse, individual differences are large, and the course of the disease is prolonged, which may affect the quality of life of patients at least, and affect the long-term survival at worst. Among them, oral cGVHD is the most common type, which mainly presents with lichen planus, oral ulcers, mucosal atrophy, erythema and pain. At present, the treatment of oral cGVHD is based on systemic treatment and local hormone-containing gargling solution and local photochemotherapy [3]. The former is prone to be complicated by local oral fungal infection, while the latter has no such equipment in China at present. Therefore, it is urgent to establish a simple, effective and low-toxicity local treatment for oral cGVHD.

Recent studies have found that the expression of Th2 cytokines (such as IL-4 and IL-5) is associated with a large number of T lymphocyte infiltration and severe tissue damage in oral lesions of patients with cGVHD, and is involved in the occurrence and development of oral cGVHD [4]. Inhibiting the accumulation and secretion of Th2 cells in the oral cavity may be an effective method to treat oral cGVHD. mesenchymal stem cells (MSCs) are a kind of pluripotent stem cells with the ability of self-renewal and multidirectional differentiation [5]. It is one of the most widely used cell products in clinic at present. Combined application with hematopoietic stem cells can improve the success rate of transplantation and accelerate hematopoietic reconstruction [6]. The applicant team previously completed a national multi-center clinical study on MSCs prevention of cGVHD, which proved that sequential infusion of MSCs can effectively reduce the incidence of cGVHD, and the mechanism is that MSCs regulate Th1: Th2 balance and promote the differentiation of T cells to Th1 direction [7]. Our previous mechanism study provides an important theoretical basis for MSCs treatment of oral cGVHD. According to the clinical needs and the rich experience of our research group in the field of MSCs clinical research, we plan to use dressing containing MSCs for the local treatment of oral cGVHD, so as to improve the lesion degree of oral cGVHD and improve the quality of life of allo-HSCT patients, and provide clinical experience for reference for the local treatment of MSCs graft-versus-host disease.

## 2. Clinical Trial Objective

Local treatment of oral cGVHD with MSCs dressing can improve the lesion degree of oral cGVHD and improve the quality of life of allo-HSCT patients.

## 3. Clinical Trial Design

To design a single-center, prospective, open, self-controlled clinical trial to explore the efficacy of human umbilical cord mesenchymal stem cell dressings in the treatment of chronic oral graft-versus-host disease.

## 4. Study Population

### 4.1 Number of Cases

A total of 38 patients will be enrolled.

Paired Wilcoxon sign-rank test was used: unilateral test  $\alpha=0.05$ ,  $1-\beta=0.9$ , superior efficacy limit  $\delta=1$ , actual difference between groups  $\delta=1.4$ , and paired difference standard deviation  $\sigma=0.7$ . Calculated  $n=30$ , according to the 20% shedding rate, the actual sample size needs  $N=38$ .

#### Paired Wilcoxon Signed-Rank Tests for Superiority by a Margin

##### Numeric Results

Higher Means are Better  
Hypotheses:  $H_0: \delta \leq SM$  vs.  $H_1: \delta > SM$   
Data Distribution: Normal

Power	N	Superiority Margin SM	Mean of Paired Differences $\delta_1$	Standard Deviation $\sigma$	Alpha	Beta
0.9035	30	1	1.4	0.7	0.05	0.0965

##### Dropout-Inflated Sample Size

Dropout Rate	Sample Size N	Dropout-Inflated Enrollment Sample Size N'	Expected Number of Dropouts D
20%	30	38	8

**Version: v1.0**

**Date: September 13, 2023**

#### **4.2 Inclusion Criteria**

The following criteria must be met for patient inclusion:

Allo-HSCT occurrence score  $\geq 2$  points in patients with oral cGVHD (refer to 2014NIHcGVHD standards and 2021cGVHD expert consensus), and met the following inclusion criteria:

Patients undergoing allogeneic hematopoietic stem cell transplantation. Both genders, aged  $\geq 18$  and  $\leq 60$ .

Karnofsky Performance Status (KPS) score  $>60$ , estimated survival period  $>3$  months. No severe systemic impairment of vital organ function.

No contraindications to other hematopoietic stem cell transplantation. Voluntary participation and informed consent.

#### **4.3 Exclusion Criteria**

Patients meeting any of the following criteria are not eligible for inclusion: Severe heart, kidney, or liver dysfunction.

Patients requiring treatment for other malignancies.

Clinical symptoms of brain dysfunction or severe psychiatric disorders that affect comprehension or compliance with the study protocol.

Patients unable to complete the required treatment plans and follow-up observations. Patients with severe acute allergic reactions.

Clinically uncontrolled active infections.

Patients currently participating in other clinical trials.

Participants deemed unsuitable for the clinical trial by the researchers.

#### **4.4 Criteria for Removal or Dropout:**

Patients experiencing disease progression unrelated to the experimental factors or death during the treatment and follow-up period will be unable to continue the observation.

#### **4.5 Termination Criteria:**

Occurrence of severe adverse reactions or intolerability.

Participant's voluntary withdrawal.

Disease progression or relapse during the trial period.

Participants deemed unsuitable for further treatment by the researchers.

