### **5. Treatment Protocol**

#### **5.1 Methods of stem cell administration**

The patient's mouth (including buccal mucosa, tongue and lip) was applied with MSCs: MSCs ( $1 \times 10^9$ /ml) dressing was applied 4 times/day for 2 weeks.

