### **5.3 Indicator Observation**

The oral lesions of patients were recorded every 2 days during treatment and scored. Oral saliva was retained for cytokine detection (destroyed after the study); Observe and record possible complications of treatment; Whole-body cGVHD score was performed at the end of treatment to record infection status. After treatment, oral cGVHD score and systemic cGVHD score were performed every 2, 4 and 6 weeks to evaluate safety, and the changes of infection, disease status and survival were recorded.

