### **6.Evaluation criteria of curative effect**

Effectiveness evaluation: The effective criterion was to reduce the oral cGVHD score by 1 point at the end of treatment. Safety evaluation basis Safety will be measured and evaluated by daily recording of potential adverse reactions to the treatment, and patients will be tested for potential toxicity that may come from the treatment through medical history, physical examination, blood tests, etc.

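### Patients stopped early for outcome-related reasons need not be counted in the efficacy result, so this uncontrolled trial can report a completers-only effect that is biased upward

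*Protocol*

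**What the plan says.** All references are to the Protocol.

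- **Section 4.5** lists the grounds for termination. They include "Occurrence of severe adverse reactions or intolerability" and "Disease progression or relapse during the trial period", together with voluntary withdrawal and the researchers' judgement. The progression line does not say whether oral cGVHD or the underlying haematological disease is meant.
- **Section 4.4**, on removal or dropout, reads: "Patients experiencing disease progression unrelated to the experimental factors or death during the treatment and follow-up period will be unable to continue the observation".
- **Section 4.1** computes 30 patients for the paired signed-rank test and then inflates: "according to the 20% shedding rate, the actual sample size needs" 38. Its dropout table expects 8 losses.
- **Section 5.1** fixes the course of treatment: "dressing was applied 4 times/day for 2 weeks".
- **Section 5.3** sets the scoring: "The oral lesions of patients were recorded every 2 days during treatment and scored". Further scores follow after treatment.
- **Section 6** defines success: "The effective criterion was to reduce the oral cGVHD score by 1 point at the end of treatment". It does not say what outcome applies to a patient who stops before two weeks, or which patients form the denominator.

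**The concern.** Severe reaction, intolerance and (if cGVHD is meant) progression are related to how the patient fares on the dressing. Patients stopped for them are not a random sample of those treated. The protocol creates this group, calls part of it dropout, sizes the trial on those who remain, and fixes an endpoint that does not settle how the stopped patients count.

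Section 3 describes a single-centre, open, self-controlled study, so no comparator arm loses failures at a similar rate. Section 4.4 also makes removal depend on whether progression is unrelated to the experimental factors. That is an unblinded judgement made while the patient's course is visible. The planned mean of 1.4 lies only 0.4 above the margin of 1, so a modest amount of selective loss matters.

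**Working it through.** **Inputs (section 4.1 and its tables).** One-sided alpha 0.05, margin 1, mean paired fall 1.4, SD 0.7, N = 30, stated power 0.9035, dropout 20%, enrolled 38, expected losses 8.

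**1. The plan's own figures.** The shift is 1.4 − 1 = 0.4, with SD 0.7. The noncentral t power at n = 28 is 0.9035, the stated value. The normal-data Wilcoxon adjustment gives 28 × π/3 = 29.3, rounded up to 30. Simulation of the signed-rank test at 30 gives 0.910. The inflation is 30/(1 − 0.2) = 37.5, rounded up to 38. The figures reproduce.

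**2. Mean fall over all enrolled.** Assume 30 completers with mean fall 1.4 and all 8 losses stopped patients with mean fall x. The mean over 38 is (30 × 1.4 + 8x)/38.

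| x | mean over 38 |
|---|---|
| 0 | 42/38 = 1.11 |
| −0.5 | 38/38 = 1.00 |
| −1 | 34/38 = 0.89 |

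**3. Effective rate.** With a normal fall, P(fall ≥ 1) = 1 − Φ((1 − 1.4)/0.7) = 0.716, or 21.5 of 30. With the 8 counted as not effective, the rate is 21.5/38 = 0.565. If the score moves in whole points, so that the cut is nearer 0.5, the completers' rate is about 90% and becomes 0.90 × 30/38 = 71%. Either way the factor is 30/38 = 0.79.

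**4. False-positive rate of a completers-only test.** Suppose the true mean over all 38 is exactly 1 and k stopped patients have zero change. The completers' mean is then 38/(38 − k), and they are tested against 1 with a one-sided 0.05 signed-rank test (simulation, SD 0.7).

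| k | completers' mean | rejection rate |
|---|---|---|
| 2 | 38/36 = 1.06 | about 11% |
| 4 | 38/34 = 1.12 | about 24% |
| 8 | 38/30 = 1.27 | about 63% |

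Repeat simulations moved these by a point or two. The nominal rate is 5%.

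**5. Power if stopped patients are kept.** Completers have mean 1.4 and SD 0.7, k patients have zero change, and all 38 are analysed.

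| k | mean over 38 | power against margin 1 |
|---|---|---|
| 2 | 1.33 | about 0.85 |
| 4 | 1.25 | about 0.61 |
| 8 | 1.11 | about 0.06 |

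The protocol does not say how many losses will be failures. The value of k and the zero change are assumptions, and k = 8 is the worst case that the planned dropout allows.

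**The case against.** The strongest reply is that analysis sets and the handling of early stoppers commonly belong in the SAP, which is not shown, and that no section states a wrong rule. This stands in part: a missing analysis-set definition alone would be no finding. But the success criterion, the stopping and removal rules and the evaluable number are all fixed in this protocol, and together they leave the endpoint open to more than one result for the same patient.

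A reader might infer that a stopped patient cannot count as a failure. The text does not say so. The end of treatment can be read as the patient's own last treatment day, and with two-daily scoring a value would usually exist. A patient whose mouth is worsening would then fail the 1-point criterion. The protocol permits this reading but does not require it.

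A reader might also infer that scores taken after rescue therapy are credited to the dressing. The protocol mentions no rescue. Systemic and local treatments appear only as background in section 1. That inference has no basis in the text and is not part of this point.

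Three further cautions stand:

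- Section 4.4 limits removal to unrelated progression and death, and section 4.5 does not say that its terminations leave the analysis.
- Voluntary withdrawal, or relapse of the underlying disease, is not evidently a failure of an oral dressing.
- The 20% is a routine allowance with no reasons attached, and section 7 expects no significant adverse reactions, so 8 failures is an upper bound and not a forecast.

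**Conclusion.** The concern holds in a limited form. The protocol allows outcome-related stoppers to be treated as dropouts, and nothing in section 6 requires them to count. A result produced that way is biased upward if stopped patients do worse than completers. That is likely for progression of cGVHD and less certain for the other reasons.

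Under the worst-case assumption of 8 zero-change failures, the overstatement is 1.4 − 1.11 = 0.29 points in the mean and about 15 percentage points in the effective rate. With only 2 such failures, the completers-only test already rejects at about twice its nominal rate. The documents do not show that the sponsor intends to drop these patients; the problem is that the endpoint as written lets it happen. The change should be made.

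**What to change.** In section 6:

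1. State that the denominator for the effective rate is all treated patients.
2. Count a patient terminated under section 4.5, or removed under section 4.4, before the 2-week score as not effective.
3. Define the end of treatment for early stoppers as the oral score on the stopping day or, failing that, the last two-daily score. Use it as their value in the paired difference.
4. Keep the completers analysis as a sensitivity analysis.

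The rate and the mean then treat an early stopper differently: the rate counts stopping as non-response, while the mean uses the score reached. The text should say that this is deliberate. It should also say that the rule covers voluntary withdrawal, where counting non-response is a conservative choice.

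Sections 4.4 and 4.5 overlap on progression and must be reconciled, including which disease is meant. Who is stopped remains for the protocol and the clinicians to decide.

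In section 4.1, state that the 0.90 power applies to completers with a mean fall of 1.4 and that it drops once zero-change patients are kept, or recheck the sample size on that basis.

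The cost is a few sentences and, at most, one extra score per early stopper, which fits the existing schedule. The downside is a less favourable reported effect and lower stated power.

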### **5. Treatment Protocol**

#### **5.1 Methods of stem cell administration**

The patient's mouth (including buccal mucosa, tongue and lip) was applied with MSCs: MSCs ( $1 \times 10^9$ /ml) dressing was applied 4 times/day for 2 weeks.

#### **5.2 Raw materials and preparation process of stem cell dressing**

**Version: v1.0**

**Date: September 13, 2023**

(1) Raw materials: The absorbable gelatin sponge commonly used in clinic is used as the raw material for dressing. In clinic, gelatin sponge has been widely used in local hemostasis including the mouth, nasal cavity and other parts.

(2) Ingredients: Absorbable gelatin sponge is a collagen product with a protein content of 70%.

(3) Properties: white or yellowish, light, soft and porous sponge, with water absorption; Although it is rubbed heavily, it will not crumble and is insoluble in water.

(4) Usage and dosage: MSCs ( $1 \times 10^9$ /ml) solution was dropped on the surface of gelatin sponge, and then applied locally to the oral lesions, so that MSCs could stay in the lesions for a longer time and better play the role of MSCs in the treatment of chronic oral graft versus host disease.

(5) Specifications: According to the size of the lesion, there are two specifications to choose from: ①  $3\text{cm} \times 3\text{cm} \times 1\text{cm}$ ; ②  $2\text{cm} \times 2\text{cm} \times 1\text{cm}$ .

### **5.3 Indicator Observation**

The oral lesions of patients were recorded every 2 days during treatment and scored. Oral saliva was retained for cytokine detection (destroyed after the study); Observe and record possible complications of treatment; Whole-body cGVHD score was performed at the end of treatment to record infection status. After treatment, oral cGVHD score and systemic cGVHD score were performed every 2, 4 and 6 weeks to evaluate safety, and the changes of infection, disease status and survival were recorded.

### **6.Evaluation criteria of curative effect**

Effectiveness evaluation: The effective criterion was to reduce the oral cGVHD score by 1 point at the end of treatment. Safety evaluation basis Safety will be measured and evaluated by daily recording of potential adverse reactions to the treatment, and patients will be tested for potential toxicity that may come from the treatment through medical history, physical examination, blood tests, etc.

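### The only effectiveness criterion (section 6, a 1-point fall) is not the hypothesis that the sample size was calculated for (section 4.1, a mean fall above 1 point), so the stated 90% power does not cover it

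*Protocol*

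**What the plan says.** - **Protocol section 6** has one sentence on efficacy: "The effective criterion was to reduce the oral cGVHD score by 1 point at the end of treatment". It does not say whether this applies to each patient or to the group, or whether a larger fall also counts.
- **Protocol section 4.1** sets a one-sided alpha of 0.05, power of 0.9, a "superior efficacy limit" of 1, an expected difference of 1.4 and a paired-difference SD of 0.7.
- **The table under section 4.1** is headed "Paired Wilcoxon Signed-Rank Tests for Superiority by a Margin". Its null hypothesis is that the difference is at most the margin, with "Data Distribution: Normal". It reports power 0.9035 at N = 30, and enrolment of 38 after 20% dropout.
- **Protocol section 8** names the paired t-test, or the Wilcoxon signed-rank test for non-normal data, with a 95% confidence interval for the difference in cGVHD score. It mentions no margin.

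Section 4.1 does not name the variable behind its paired difference. That it is the oral cGVHD score is an inference from the section 6 criterion, the score difference in section 8 and the before-and-after self-control in section 9.

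**The concern.** The value of 1 point appears twice in different roles. In section 6, reaching it is what makes the treatment effective. In section 4.1 it is the boundary of the null hypothesis, which the mean fall must exceed. The protocol does not connect the two uses.

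This matters for what the trial can conclude. The sample size and the 90% power belong entirely to the margin test. A reader who follows section 6 would judge the dressing by how many patients fell by 1 point, a quantity for which no power was calculated and which can look favourable when the mean fall does not exceed the margin. The trial is open, single-centre and self-controlled (section 3), with no concurrent control group to put a high response percentage in context.

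**Working it through.** **Inputs.** From section 4.1 and its table: margin 1, expected mean fall 1.4, SD 0.7, one-sided alpha 0.05, n = 30, normal differences. From section 6: the 1-point criterion, read here as a fall of at least 1. Whole-point scoring is an assumption, so results are given with and without it.

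**1. The plan's own figure.** The Wilcoxon test is handled by reducing n by the factor π/3 and rounding down: 30/(π/3) = 28.65, so n′ = 28 with 27 degrees of freedom. The noncentrality is √28 × (1.4 − 1)/0.7 = 3.02. Noncentral t power, one-sided at 0.05, is 0.9035, which matches the table. Dropout: 30/0.8 = 37.5, rounded up to 38, also a match. The arithmetic of section 4.1 is sound.

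**2. The sample size depends on the margin.** By the same method without rounding n′, a one-sided test of a 1.4-point fall against zero has power 0.886 with 4 patients and 0.966 with 5. So n = 30 follows from testing against 1.

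**3. Share of patients meeting section 6, by true mean fall m.** For a continuous score, P(fall ≥ 1) = 1 − Φ((1 − m)/0.7). For a score rounded to whole points, P = 1 − Φ((0.5 − m)/0.7).

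| True mean fall m | Effective, continuous | Effective, whole points | Chance that the section 4.1 test succeeds, n = 30 (continuous) |
|---|---|---|---|
| 1.0 | 1 − Φ(0) = 50% | 1 − Φ(−0.714) = 76% | 5% |
| 1.4 | 1 − Φ(−0.571) = 72% | 1 − Φ(−1.286) = 90% | 90% (0.9035) |

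At m = 1.4 on a whole-point score, the share falling by exactly 1 is Φ(0.143) − Φ(−1.286) = 46%. These patients are effective under section 6 but have zero difference from the margin under section 4.1.

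**4. What the margin test needs.** With an observed SD of 0.7 and a one-sided t-test, the observed mean fall must exceed 1 + 1.699 × 0.7/√30 = 1.22.

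**5. A constructed 30-patient example.** Suppose 21 patients fall by 1 point, 5 by 2 and 4 by 0.

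- Section 6: 26/30 = 87% effective.
- Mean fall: (21 + 10)/30 = 1.03.
- t-test against 1: the SD is 0.556, so the standard error is 0.556/√30 = 0.1015. Then t = 0.0333/0.1015 = 0.33 on 29 degrees of freedom, one-sided p = 0.37.
- Exact signed-rank test against 1: the 21 zeros drop out, leaving nine differences of equal size, five of them positive. P(X ≥ 5) for a binomial with 9 trials and probability 0.5 is 0.50.

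An 87% effective rate therefore sits beside a margin test that shows nothing.

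**The case against.** The strongest reply is that the two sections work at different levels. Section 6 most naturally defines response in a single patient, and section 4.1 tests a group mean. Using the smallest worthwhile change as the superiority margin is ordinary practice, and any trial with both a response rate and a mean test can give differing impressions from the same data. This stands. A reader might infer that the sections give opposite definitions of success, so that the same data are a success under one and a failed trial under the other. The documents do not support that. Section 6 does not say that it is a trial-level rule, and section 4.1 is a sample-size calculation that nowhere calls a missed margin a failure.

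A reader might also count the absence of a required response proportion as an error, or infer that the favourable rule will be picked after the data are seen. Neither follows. A statistical analysis plan may exist and may settle both, so the missing proportion taken alone is only missing detail.

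Two further cautions are fair. The 76%, 90% and 46% figures need whole-point scoring, which the protocol does not state. The 30-patient data set was chosen to illustrate the point.

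What the objection leaves untouched is that the protocol's only effectiveness criterion and its only powered hypothesis are different quantities, and nothing in the document joins them.

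**Conclusion.** The point holds as a mismatch between the effectiveness criterion and the hypothesis that fixes the sample size. Followed as written, the trial can be called effective on a rule to which its stated power of 0.9035 does not apply. At a true mean fall of exactly 1.0, where the mean does not exceed the margin, about half of patients (about three quarters on a whole-point score) would count as effective, against about a 5% chance of passing the section 4.1 test.

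This rests on the protocol's SD of 0.7, normally distributed falls, reading section 6 as a fall of at least 1 point per patient, and the inference that section 4.1 concerns the oral cGVHD score. If section 6 is meant for the group instead, the tension is more direct: a mean fall of exactly 1 would be effective there and lie on the null boundary in section 4.1. The sample-size calculation itself is correct. The change should be made because it decides what the trial can conclude.

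**What to change.** 1. In section 6, state that the efficacy conclusion rests on the fall in oral cGVHD score from before treatment to the end of treatment, tested one-sided at 0.05 against the 1-point margin of section 4.1.
2. In section 4.1, name that fall as the paired difference.
3. In section 8, carry the same margin into the paired test, so that the comparison is with 1 and not with 0.
4. Reword the 1-point criterion as a per-patient response, a fall of at least 1 point, and report it as a secondary proportion with an exact confidence interval.

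This changes wording only; the sample size and assessments stay as they are. The downside for the sponsor is that a high response percentage alone can no longer be the headline result.
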